5.3.1 Rationale for Dose Titration

Dose titration has been added because data from the GBT440-001 study has shown a linear and highly significant relationship between GBT440 blood level and improvement in hemolysis and no plateau effect has been reached. This suggests that subjects may derive greater benefit at higher doses achieving higher haemoglobin occupancy. Furthermore the target for optimal efficacy based on individuals with HbS/Hereditary persistence of fetal haemoglobin is 20-30% haemoglobin occupancy (Ngo 2011) and the preliminary PK data from Cohort 17 showed that the majority of subjects did not maintain haemoglobin occupancy >20% at 900 mg daily dosing. In addition, no dose limiting toxicities or concerning dose-or exposure related toxicities pose a safety concern with higher doses. Doses of 1000 mg for 28 days and 900 mg for 90 days have been well tolerated, with the majority of AEs were Grade 1 or 2 in severity. At 1500 mg, the predicted C_{max} is 167 μ g/mL, which is less than the C_{max} already observed and found to be well-tolerated in healthy volunteers in GBT440-001 (294 μ g/mL at 900 mg [Cohort 10]).

To assess the higher dose of 1500 mg, subjects will be dose escalated by 300 mg over 2-week intervals. The principal investigator will determine if the 600 mg or the 900 mg dose is well tolerated (after at least 28 days of prior dosing), and that the subject may receive further benefit from higher dosing (further improvement in haemoglobin, reticulocyte count or unconjugated bilirubin) the dose may be increased by one capsule (300 mg) every two weeks up to a maximum of 1500 mg.

This study will be performed in compliance with the protocol, ICH GCP and applicable regulatory requirements. Aspects of the study concerned with the investigational medicinal product(s) (IMPs) will meet the requirements of EU GMP.

5.4 Risk Assessment

Based on the mechanism of action of GBT440 and findings in the nonclinical safety toxicology studies, GBT440 could cause tissue hypoxia. In GLP toxicology studies, rats dosed for 28 days with ≥ 250 mg/kg/day demonstrated increased erythropoietin and red cell mass (Hct, RBC, or Hb) with extramedullary hematopoiesis and bone marrow hypercellularity. These findings are consistent with expected physiologic compensation to hypoxia, were not considered adverse, and were reversible.

In prior clinical experience with other agents, no adverse reactions related to tissue hypoxia were reported at the highest tested doses of tucaresol administered in either healthy subjects (maximum 40% Hb-modification) or subjects with SCD (maximum 24% Hb modification), or BW12C infusions in either healthy subjects (maximum 40% Hb-modification) or subjects with SCD (23% Hb modification) ([Arya 1996](#), [Keidan 1986](#), [Nicholls 1989](#), [Rolan 1995](#)). Appropriate acute and chronic compensatory physiologic responses to tissue hypoxia were observed, including an increase in heart rate during

moderate exercise and a slight increase in reticulocyte counts at high doses ([Nicholls 1989](#), [Rolan 1995](#), [Rolan 1993](#)). Importantly, healthy subjects were well compensated- both at rest and at near maximal exercise with little change in resting heart rate ([Nicholls 1989](#)). Potential tissue hypoxia can be monitored by hematology laboratory studies, erythropoietin levels, and cardiovascular parameters.

Gastrointestinal effects (primarily emesis, and soft or liquid feces) were observed in all species and were dose-limiting in dogs and monkeys. Gastrointestinal erosions, ulcers, or epithelial hyperplasia were observed at high doses in rats.

Preliminary results from Study GBT440-001 evaluating GBT440 in adult subjects suggest that GBT440 is well tolerated in healthy subjects at single doses from 100 to 2800 mg and in subjects with SCD at a single dose of 1000 mg. The results also suggest that GBT440 is well tolerated in healthy subjects following repeat administration at dosages up to 900 mg once daily for 15 days, and in subjects with SCD following administration at dosages up to 1000 mg once daily for 28 days. The Safety Monitoring Committee (SMC) review of ongoing dosing in a 90 day treatment cohort at 700 mg and 900 mg per day has found GBT440 to be generally safe and well tolerated (as of [06 June 2016](#)). The most commonly reported AEs across all subjects principally included diarrhea and headache; these events were often considered by the Investigator to be treatment-related. In addition, the decline in erythropoietin levels suggest an improvement in oxygen delivery either by increase in hemoglobin or improvement in microvascular blood flow, or both.

5.5 Urgent safety measures

In accordance with UK Law [Medicines for Human Use (Clinical Trials) as amended: SI 1031 Part 4 Section 30] the Sponsor and Investigator may take appropriate urgent safety measures in order to protect the subjects of a clinical trial against any immediate hazard to their health or safety. If such measures are taken the Sponsor shall immediately (no later than 3 days from the date the measures are taken) give written notice to the licensing authority and the relevant ethics committee of the measures taken and the circumstances giving rise to those measures.

6.0 STUDY OBJECTIVES

6.1 Primary Objective

- To evaluate the safety and tolerability of up to a total of 6 months dosing in subjects with sickle cell disease (SCD) who participated in the GBT440-001 study.

6.2 Secondary Objectives

- To observe the pharmacokinetics (PK) of GBT440 in plasma and whole blood in subjects with SCD.
- To characterize the effect on biomarkers of hemolysis in subjects with SCD.

6.3 Exploratory Objectives

- To obtain data on exploratory markers of sickle cell disease activity.
- To obtain data on sickle cell disease symptoms.

7.0 INVESTIGATIONAL PLAN

7.1 Overall Study Design

This is an open label, single arm study.

Up to 16 subjects with SCD who were enrolled in the GBT440-001 study (Cohorts 7, 11, 12, 14, 15, 16 or 17 will be eligible to participate.. On attendance to the clinic, subjects in Cohorts 15 or 17 will be asked whether they want to be considered for study GBT440-024. If the subject is interested in study GBT440-024 all consent activities will be completed before the samples/procedures for GBT440-024 are collected/Performed. For subjects who were enrolled in Cohorts 7, 11, 12, 14, 16 or 17 who are interested in participating in study GBT440-024, all consent activities will be completed before the samples/procedures for GBT440-024 are collected/Performed. Prior to enrolment into this study the individual subject treatment allocations for eligible subjects from the GBT440-001 (Cohorts 15 or 17) will be unblinded and subjects will be assigned to the following treatment groups:

Group 1

Subjects from Cohort 17 in the GBT440-001 study who have received GBT440 900 mg per day for 4 months will continue receiving GBT440 900 mg per day for a further 2 months in this study.

Group 2

Subjects from Cohort 17 in the GBT440-001 study who have received placebo for 2 months will receive GBT440 900 mg per day for 6 months in this study.

Group 3

Subjects from Cohort 15 in the GBT440-001 study who have received GBT440 600 mg per day for 2 months will continue receiving GBT440 600 mg for a further 4 months in this study or the dose may be increased if the subject has tolerated 600 mg in GBT440-001.

Group 4

Subjects from Cohort 15 in the GBT440-001 study who have received placebo for 2 months will receive GBT440 900 mg per day for 6 months in this study.

Group 5

Subjects from Cohort 7, 11, 12, 14, 16 or 17 who received either GBT440 or placebo will receive a total of continuous 6 months of treatment with GBT440 in this study (GBT440 024) at a dose of 900 mg per day.

Subjects enrolled on this study will be numbered based on the subject number that were assigned in Study GBT440-001 with the addition of 24 to the beginning of the subject number. eg, Subject 17001 in study GBT440-001 will be assigned number 2417-1001 in this study.

Subject numbering in this study will be as follows:

GBT440-001 Cohort	GBT440-001 Subject Number	GBT440-024 Group	GBT440-024 Subject Number
17	17001-17008	1 and 2	2417-1001 to 2417-1008
15	15001-15008	3 and 4	2415-1001 to 2415-1008
7	07001-07008		2407-1001 to 2407-1008
11	11001-11016		2411-1001 to 2411-1016
12	12001-12014		2412-1001 to 2412-1014
14	14001-14008		2414-1001 to 2414-1008
16	16001-16008		2416-1001 to 2416-1008

If a subject from GBT440-001 elects not to participate in this protocol, their corresponding identification number would remain unused.

All Subjects will receive a total of 6 months treatment with GBT440 which will include treatment with GBT440 in the GBT440-001 study for subjects in Cohort 15 or 17. Subjects from Cohort 7, 11, 12, 14, 16 or 17 who received either GBT440 or placebo will receive a total of 6 months of treatment with GBT440 in this study.

A Safety Monitoring Committee (SMC) consisting of the Principal Investigator, Sponsor Medical Monitor, and Independent Safety Physician will have overall responsibility for assessing safety and tolerability. The SMC will review cumulative data at least monthly to determine whether continued dosing may proceed. The responsibilities of the SMC will be described in a separate charter.

7.1.1 Stopping Rules

Individual subject stopping rule

- Dosing for any individual subject will be stopped if the subject experiences a serious adverse event (SAE) or a clinically significant non serious AE, which in

the opinion of the Principal Investigator or Sponsor's Medical Monitor, warrants discontinuation of the study for that subject's wellbeing.

7.2 Study Population

Male/female patients with sickle cell disease will be entered into this study provided that they satisfy the following inclusion/exclusion criteria.

7.2.1 Subject Inclusion Criteria

1. Male or female subjects with HbSS, HbS/β⁰thalassemia, HbS/β⁺thalassemia, or HbSC aged 18 to 60 years inclusive and >50 kg who have enrolled in cohorts 15 or 17 of the GBT440-001 study and will not experience interruption in dosing for greater than 7 days prior to commencing continuation of dosing in this extension study protocol.
2. Male or female subjects who were enrolled in Cohorts 7, 11, 12, 14, 16 or 17 in the GBT440-001 study (and are currently off-study) are eligible to enroll into this study.
3. Subjects who if female and of child bearing potential, agree to continue to use highly effective methods of contraception prior to enrolment in this study and for 3 months after the last dose of IMP.
4. Subjects whose clinical laboratory test results are not clinically relevant and continue to be acceptable to the Investigator at the final visit of the GBT440-001 study for subjects enrolled in Cohort 15 or 17.
5. Subjects who if male are willing to continue to use barrier methods of contraception, prior to enrolment in this study to 3 months after the last dose of IMP.

7.2.2 Subject Exclusion Criteria

1. Subjects requiring chronic transfusion therapy.
2. Subjects receiving a blood transfusion within 30 days of enrolment in this study.
3. Subjects with alanine aminotransferase (ALT) or aspartate aminotransferase (AST) >5x upper limit of normal reference range (ULN)
4. Subjects with moderate or severe renal dysfunction (calculated modification of diet in renal disease estimated glomerular filtration rate (MDRD eGFR) <60mL/min/1.73 m² appropriately corrected for race and gender).

5. Subjects with any history of congestive heart failure requiring hospitalisation or whose 12 lead ECG prior to enrolment has a confirmed QTcF interval of >450 msec for male subjects or >470 msec for female subjects.
6. Subjects who do not conform to the above inclusion criteria.
7. Female subjects who are pregnant, trying to become pregnant or lactating.
8. Subjects who have a clinically relevant history or presence of respiratory, gastrointestinal, renal, hepatic, haematological, lymphatic, neurological, cardiovascular, psychiatric, musculoskeletal, genitourinary, immunological, dermatological, connective tissue diseases or disorders, or additional risk factors for torsades de pointe (e.g., heart failure, hypokalemia, personal or family history of long QTc interval).
9. Subjects who have a history of relevant atopy.
10. Subjects who have a history of relevant drug hypersensitivity.
11. Subjects who have a history of alcoholism.
12. Subjects who have a history of drug abuse (N.B. occasional recreational cannabis use is not an exclusion).
13. Subjects who consume more than 14 (female subjects) or 21 (male subjects) units of alcohol a week.
14. Subjects who have a significant infection or known inflammatory process on admission to this study.
15. Subjects who have acute gastrointestinal symptoms at the time of admission (e.g. nausea, vomiting, diarrhoea, heartburn).
16. Subjects who have an acute infection such as influenza at the time of admission.
17. Subjects (females of child-bearing potential and males) who do not agree to use contraception (as defined in Section 7.2.3.2).
18. Subjects who are vegans.
19. Subjects who cannot communicate reliably with the Investigator.
20. Subjects who are unlikely to co-operate with the requirements of the study.

7.2.3 Restrictions

- Since GBT440 is a weak inhibitor of cytochrome P450 (CYP3A4), GBT440 should be used with caution with CYP3A4 substrates with a narrow therapeutic index (refer to [Table 1](#)).
- In vitro data suggest that GBT440 could be metabolized by CYP1A1, 1B1, 2B6, 2C9, 2C19, 3A4, and 3A5. Thus strong inducers of CYP2B6, CYP2C9, CYP2C19, and CYP3A4/CYP3A5 should be prohibited (Table 2). The use of herbal medications (e.g., St. John's Wort) are not allowed.

Table 1 CYP substrates with Narrow Therapeutic Range

CYP Enzymes	Substrates with narrow therapeutic range*
CYP3A4	alfentanil, astemizole, cisapride, cyclosporine, dihydroergotamine, ergotamine, fentanyl, pimozide, quindine, sirolimus, tacrolimus, terfenadine
CYP2C8	None

*Substrates with narrow therapeutic range refers to drugs whose exposure-response relationship indicates that small increases in their exposure levels by the concomitant use of CYP-inhibitors may lead to serious safety concerns.

Adapted from: FDA DRAFT Guidance for Industry: Drug Interactions Studies-Study Design, Data Analysis, Implications for Dosing, and Labeling Recommendations. February 2012.

Table 2: Strong CYP Inducers

CYP	Strong Inducers
CYP3A4/3A5	Aavasimibe, carbamazepine, phenytoin, rifampin, St. John's wort
CYP2B6, CYP2C9, CYP2C19	currently no known inducers

Please note the following: This is not an exhaustive list. For an updated list, refer to the following link:
<http://www.fda.gov/Drugs/DevelopmentApprovalProcess/DevelopmentResources/DrugInteractionsLabeling/ucm080499.htm>.

- During the study, male subjects should continue to avoid consuming more than 3 units of alcohol per day and female subjects should continue to avoid consuming more than 2 units of alcohol per day.
- Subjects will be required to abstain from blood or plasma donation until 3 months after the final medical examination at the study clinic follow up.

If a subject does not comply with these restrictions or tests positive to any laboratory tests (e.g. drug, alcohol) they may be excluded or withdrawn from the study.

7.2.3.1 Avoidance of Pregnancy

Women of Child Bearing Potential

Pregnancy should be avoided by either true abstinence or the use of highly effective means of contraception (see Section 7.2.3.2) for the duration of the study and a total period of 3 months after the subject has taken the last dose of GBT440.

In order to include women of child bearing potential in any clinical trial, certain precautions pertaining to pregnancy must be taken. These will include serum pregnancy testing at enrollment and urine pregnancy test at the times indicated in Table 4, Table 5 and Table 6.

Female subjects who become pregnant during a study will be withdrawn.

Women of Non-Child Bearing Potential

Female subjects of non-child bearing potential are defined as; bilateral oophorectomy / hysterectomy/ post-menopausal females being amenorrhoeic for greater than 2 years with an appropriate clinical profile, e.g. age appropriate, history of vasomotor symptoms.

Instructions for Male Subjects

There is no information about effects that GBT440 could have on the development of the foetus in humans. Therefore, it is important that the partners of male subjects do not become pregnant during the study and for a total period of 3 months after the male subject has taken the last dose of GBT440.

As a precaution, all male subjects should avoid fathering a child by either true abstinence or the use of barrier methods of contraception (see Section 7.2.3.2).

As there is no information for GBT440 being secreted in the ejaculate, male subjects (including men who have had vasectomies) whose partners are currently pregnant should use barrier methods for the duration of the study and for 3 months afterwards. This is to ensure that the foetus is not exposed to the IMP in the ejaculate.

7.2.3.2 Acceptable Forms of Contraception

Highly effective methods of birth control are defined as those which result in a low failure rate (i.e. less than 1% per year) when used consistently and correctly.

- Combined (estrogen and progestogen containing) hormonal contraception associated with inhibition of ovulation:
 - Oral
 - Intravaginal

- Transdermal

Hormonal contraception must be supplemented with a barrier method (preferably male condom).

- Progestogen-only hormonal contraception associated with inhibition of ovulation:
 - Oral
 - Injectable
 - Implantable

Hormonal contraception must be supplemented with a barrier method (preferably male condom).

- Intrauterine device (IUD)
- Intrauterine hormone-releasing system (IUS)
- Bilateral tubal occlusion
- Vasectomised partner. Note that vasectomised partner is a highly effective birth control method provided that partner is the sole sexual partner of the woman of child bearing potential trial participant and that the vasectomised partner has received medical assessment of the surgical success.
- Sexual abstinence. Sexual abstinence is considered a highly effective method only if the subject is refraining from heterosexual intercourse during the entire period of risk associated with the study treatments. The reliability of sexual abstinence needs to be evaluated in relation to the duration of the clinical trial and the preferred and usual lifestyle of the subject.

For male subjects:

- Barrier methods of contraception: condom or occlusive cap (diaphragm or cervical/vault caps) with spermicidal foam/gel/film/cream/suppository. The use of barrier contraceptives should always be supplemented with the use of a spermicide. The following should be noted:

7.2.3.3 Time Period for the Collection of Pregnancy Information

All pregnancies in female subjects and the female partners of male subjects receiving at least one dose of IMP will be recorded from first dose to 3 months after the final dose.

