7.2.3.4 Follow-up in the Event of a Pregnancy

If a female subject, or the female partner of a male subject, who has received IMP becomes pregnant, the pregnancy will be recorded. The ethics committee and the Sponsor will be informed. The subject will be asked to provide information on the outcome of the pregnancy, including premature termination should the case arise.

Spontaneous miscarriage and congenital abnormalities will be reported as SAEs.

The follow-up period will be deemed to have ended when the health status of the child has been determined at birth.

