- f: PK samples will be drawn pre dose. If the dose is increased to 1500 mg, please collect the following timepoints: pre dose, then 1-4 hours, 6-8 hours and 24 hours post dose on study visit days of Day 15 (± 3 days), Day 60 (± 3 days) and Days 90 (± 3 days) of receiving 1500 mg.g: Days 15 and 45 are only to be conducted if the dose is increased to 1500 mg.
- h: Can be omitted if measurements were collected in the past 7 days as part of the GBT440-001 study.

Table 5 Schedule of Assessments for Groups 2, 4 and 5

Groups 2: Subjects from Cohort 17 in the GBT440-001 study who have received placebo for 4 months will receive GBT440 900mg per day for 6 months

Group 4: Subjects from Cohort 15 in the GBT440-001 study who have received placebo for 2 months will receive GBT440 900 mg per day for 6 months

Group 5: Subjects with SCD from Cohorts 7, 11, 12, 14, 16 or 17 in the GBT440-001 study will receive GBT440 900 mg per day for 6 months

Assessments	Enrolment a	Baseline for Cohort 7,11,12,14, 16 or 17 (within 7 days of Day 1)	Outpatient Treatment Period											
			1 +/-3 days a	15 +/-3 days	30 +/-3 days	45 +/-3 days	60 +/-3 days	90 +/-3 days	120+/-3 days	150+/-3 days	180 +/-3 days	187+/-3 days	194 +/-5 days	208 End
Day number	Last treatment day GBT440-001 (+6 days) Cohorts 15 and 17													
Visit number	0		1	2	3	4	5	6	7	8	9	10	11	12
Informed consent	X	X												
Eligibility assessment	X	X												
Medical History	X	X												
Physical examination b	X	X		X	X		X	X	X	X	X			X
Weight	X	X		X	X	X	X	X	X	X	X			X
Vital signs	X	X	X	X	X	X	X	X	X	X	X			X
12 Lead ECG (single) c	X	X			X		X	X	X	X	X			
Drug administration d				X-----							X			
Adverse events				X-----										X
Urinalysis e	X	X						X	X	X	X			X
Urine microalbumin/creatinine	X	X						X			X			
Haematology e	X	X		X	X	X	-	X	X	X	X			X
Serum biochemistry e	X	X		X	X	X	X	X	X	X	X			X
Coagulation e	X	X		X		X		X	X	X	X			X
Pregnancy test (females only)	X	X			X		X	X	X	X	X			X
Haemoglobin electrophoresis		X						X			X			X
PK samples (plasma and whole blood) f	X			X	X		X	X	X	X	X	X	X	X
Serum erythropoietin	X ^h	X			X		X	X	X	X	X			X
Exploratory plasma biomarkers	X ^h	X			X		X	X	X	X	X			X

Assessments	Enrolment a		Outpatient Treatment Period											
			1 +/-3 days	15 +/-3 days	30 +/-3 days	45 +/-3 days	60 +/-3 days	90 +/-3 days	120+/-3 days	150+/-3 days	180 +/-3 days	187+/-3 days	194 +/-5 days	208 End

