Day number	Last treatment day GBT440-001 (+6 days) Cohorts 15 and 17	Baseline for Cohort 7,11,12,14, 16 or 17 (within 7 days of Day 1)	a											
Dense cells	X ^h	X			X		X	X	X	X	X			X
Carboxyhaemoglobin	X ^h	X						X			X			X
HbA1c	X	X						X			X			X
NT-proBNP	X ^h	X						X			X			X
Concomitant medication diary		X	X-----											X

Key

Note: Visit 0 is the last treatment day for subjects in GBT-440-001 (Day 118 for Cohort 17 and Day 60 for Cohort 15)

- a: Enrolment and visit 1 may be combined. On admission to the clinic the subjects will be asked whether they want to be considered for study GBT440-024. If the subject is interested in being enrolled on study GBT440-024 all consent activities will be completed before the samples/procedures for GBT440-001 or GBT440-024 are collected/Performed. Visit 0 (enrolment visit) is the last day of treatment in GBT440-001, which can be 6 days before Visit 1. If the last day of treatment in GBT440-001 (Day 118 or Day 60 for Cohort 17 and Cohort 15) – the enrolment visit is not being repeated as standalone visit.
- b: Complete physical examination on enrolment, a limited physical examination on all other days. Directed physical examinations will be performed as required.
- c: 12 lead ECG (single) will be performed within 30 minutes prior to dose
- d: GBT440 900mg(three capsules) for Group 2 and GBT 440 600mg (2 capsules) for Group 4 and GBT440 900 mg (3 capsules) for Group 5 will be administered daily in the morning. On days when PK samples are drawn GBT 440 should be administered after an overnight fast.
- During the dosing period, subjects will be contacted every week in between outpatient visits to confirm GBT440 administration and subject well being.
- e: Additional samples will be collected if clinically indicated
- f: PK samples will be drawn pre dose. If the dose is increased to 1500 mg, please collect the following timepoints: pre dose, then 1-4 hours, 6-8 hours and 24 hours post dose on study visit days of Day 15 (±3 days), Day 60 (±3 days) and Days 90 (±3 days) of receiving 1500 mg.
- h: Can be omitted if measurements were collected in the past 7 days as part of the GBT440-001 study.

Table 6 Schedule of Assessments Group 3

Group 3: Subjects from Cohort 15 in the GBT440-001 study who have received GBT440 600 mg per day for 2 months will continue receiving GBT440 600 mg per day for a further 4 months (the dose may be increased if the subject tolerated 600 mg in GBT440-001).

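### Pregnancies are to be recorded to 3 months after the last dose, but no contact or test is scheduled after 28 days, leaving about 69% of the post-dose period to spontaneous report

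*Combined protocol and SAP*

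**What the plan says.** Protocol Section 7.2.3.3 covers "All pregnancies in female subjects and the female partners of male subjects receiving at least one dose of IMP" and says that these "will be recorded from first dose to 3 months after the final dose". Section 7.2.3.1 sets the same horizon for contraception: women of childbearing potential are to avoid pregnancy "for the duration of the study and a total period of 3 months after the subject has taken the last dose of GBT440", and partners of male subjects are likewise not to become pregnant until 3 months after his last dose.

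Detection is described in two places. Section 7.2.3.1 provides for a serum test at enrolment and a "urine pregnancy test at the times indicated in Table 4, Table 5 and Table 6". The keys to the schedules add regular contact, but only while subjects are on drug; in Tables 5 and 6 the wording is "During the dosing period, subjects will be contacted every week in between outpatient visits to confirm GBT440 administration". Section 8.4 also ties weekly contact to the outpatient dosing periods.

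Section 7.2.3.4 deals with a pregnancy once it is known. It is recorded, the sponsor and the ethics committee are told, follow-up runs to birth, and "The subject will be asked to provide information on the outcome of the pregnancy". Miscarriage and congenital abnormality are reported as SAEs.

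**The concern.** The recording period and the schedule of contacts do not match. The protocol commits to a complete count of pregnancies over 3 months after dosing, but the last planned occasion to test or ask comes 28 days after dosing. Section 7.2.3.4 says what to do with a known pregnancy, not how one would come to light after the End visit. Partners are not tested at any time, and no schedule row asks about them, so their pregnancies depend on the male subject's report throughout.

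Safety is the primary objective (Section 6.1). Section 7.2.3.1 acknowledges that the drug's effect on human foetal development is unknown, and Section 5.1.5 reports only dose range-finding embryo-fetal studies, which showed nothing notable. Because Section 7.2.3.4 makes some pregnancy outcomes SAEs, a pregnancy that is not learned of can also mean an SAE that is not reported. Without a contact at the end of the period, the study report could not say that pregnancy status was established for it.

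**Working it through.** The protocol gives durations but no coverage figure, so there is nothing to reproduce. The check is day arithmetic.

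**Inputs**
- Recording period after the last dose: 3 months (Section 7.2.3.3). No day count is given; I take 91 days and vary it from 90 to 92.
- Last dosing day *L* and End visit *E*, from Tables 4, 5 and 6.
- Allowance on the last dosing visit: ±3 days. None is shown for the End visit.

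**Step 1. Last dose to last visit, *E* − *L***

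| Schedule | Groups | *L* | *E* | Gap (days) |
|---|---|---|---|---|
| Table 4 | 1 | 60 | 88 | 28 |
| Table 5 | 2, 4, 5 | 180 | 208 | 28 |
| Table 6 | 3 | 120 | 148 | 28 |

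**Step 2. Share of the post-dose period without scheduled contact, (*W* − gap)/*W***
- *W* = 90: 62/90 = 68.9%
- *W* = 91: 63/91 = 69.2%
- *W* = 92: 64/92 = 69.6%

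With *L* moved by ±3 days the gap is 25 to 31 days. The extremes are (90 − 31)/90 = 59/90 = 65.6% and (92 − 25)/92 = 67/92 = 72.8%.

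**Step 3. Share of the full period from first dose, 63/(*L* − 1 + 91)**, counting from Day 1 of this study
- Group 1: 63/(59 + 91) = 63/150 = 42%
- Group 3: 63/(119 + 91) = 63/210 = 30%
- Groups 2, 4 and 5: 63/(179 + 91) = 63/270 = 23%

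**Step 4. What could fill the 63 days.** Weekly contact ends with dosing. The last pregnancy test in each table is at the End visit. No later call, home test or visit appears in Sections 7.2.3, 8, 9 or 17.0. For early leavers, Section 7.2.4 asks for observations up to the date of withdrawal and mentions a follow-up visit only after withdrawal for an AE, whereas Section 7.2.3.3 applies to anyone who took one dose.

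**Step 5. How many events.** As an upper bound, put all 16 subjects (or their partners) at risk.
- At the 1% per year ceiling that Section 7.2.3.2 gives for highly effective methods: 16 × 0.01 × 63/365 = 0.03 pregnancies in the uncovered days.
- At 10% per year (my assumption for barrier methods; the protocol has no figure): 16 × 0.10 × 63/365 = 0.28.

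This counts conceptions falling within the 63 days. It leaves out earlier conceptions that are recognised only after the End visit.

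**The case against.** The other side has four fair points.

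- **No scheduled contact is not the same as no means of capture.** A subject can report a pregnancy unprompted, and Section 7.2.3.4 provides for recording it outside the visit tables. An instruction to report would naturally sit in the consent form, which is not part of the review copy, and the advice to male subjects in Section 7.2.3.2 breaks off there. A reader might infer that nothing could pick up a pregnancy after the End visit; the documents do not support that. What remains is that self-report is passive: no report may mean no pregnancy or no report made.
- **Two-thirds is a share of the post-dose part only.** The period in Section 7.2.3.3 starts at the first dose, so reading 69% as the share of that whole period is wrong. Step 3 gives 23% to 42%.
- **Conceptions on drug in female subjects are largely covered.** The End visit includes a pregnancy test 28 days after the last dose. This stands, and it narrows the gap to washout conceptions (including those too recent to show at the End visit) and partner pregnancies not yet known.
- **Few events are expected, and no planned analysis in Section 12 uses them.** This also stands and limits the weight of the point. It does not remove the mismatch, since the purpose is to learn of individual cases.

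**Conclusion.** Section 7.2.3.3 and Tables 4, 5 and 6 need to be reconciled. About 63 of roughly 91 post-dose days (69%; 66% to 73% with the visit allowance and a 90 to 92 day period) have no scheduled contact, test or reporting step in the text available, in all five groups. As a share of the period from first dose in this study, this is 42%, 30% and 23% for Group 1, Group 3 and Groups 2, 4 and 5. It would be smaller for Groups 1 and 3 if earlier active dosing in GBT440-001 were counted.

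A reader might go further and conclude that the schedule cannot deliver pregnancy safety data. That is too strong, since all of dosing and the following 28 days are covered by visits, with tests for female subjects. The supported conclusion is that the last two months of the period rest on spontaneous report, which cannot confirm that no pregnancy occurred. This is a minor correction to safety capture.

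It assumes that dosing runs to the nominal last day and that no active contact is arranged in text not available here. A subject who stops dosing early but keeps attending visits would be covered for longer.

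**What to change.** Keep Section 7.2.3.3 as written and add to Tables 4, 5 and 6 one telephone contact at or shortly after 3 months from the last dose, asking about pregnancy in the subject or the subject's partner. Placing it slightly after the 3-month point helps with conceptions late in the period that are not yet recognised, though no single call will catch them all. Apply it also to subjects who stop early, counted from their own last dose, unless they have declined further contact. If the consent form already asks subjects to report pregnancies, refer to that in Section 7.2.3.3; the call then confirms what self-report cannot.

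The cost is at most 16 short calls by a site that already telephones its subjects. Each subject's record stays open about 2 months longer (63 days), which also delays final closure of the pregnancy data. No visit, sample or procedure is added.
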